9.2.2 Drop-Out Subjects

Once a subject is dropped out from the study, no further information for that subject will be collected. However, the reason for drop-out will be reported and serious adverse events will be reported to AbbVie until 30 days following the intake of the last dose of adalimumab.

Subjects will be dropped out from the study:

- 1) If the subjects choose to withdraw from the study
- 2) Where ethical or practical conflicts hinder the procedure of the study, and such cases will be determined based on the investigator's judgment
- 3) In case of Adalimumab discontinuation at any point during study period

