9.3 Variables

Participating subjects will be followed up at week 12, 28, 36, and 52 for 12 months after baseline. At baseline, demographics, disease and medication related data, the presence of extra-axial symptoms such as peripheral arthritis, enthesitis and dactylitis will be collected.

On every follow-up visit, BASDAI 50 will be measured to observe the effectiveness of AS. Also, the change of MASES, TJC_s (0 to 46), SJC_s (0 to 44), Dactylitis score and the presence of plantar fascia will be evaluated to investigate the effectiveness of adalimumab on EAMs.

After baseline visit, if subjects have extra-axial symptoms other than Enthesitis, Peripheral arthritis and Dactylitis, relevant data will be collected.

Enthesitis is defined as at least 1 inflamed enthesis in the Maastricht Ankylosing Spondylitis Enthesitis Score (MASES, 0 to 13) or of the plantar fascia of the foot. Peripheral arthritis is defined as at least 1 of swollen joint counts (SJC, 0 to 44, excluding hip joints). Dactylitis will be measured by a simple count of dactylitic digits.

Patients will be administered adalimumab 40 mg every other week in addition to their preexisting anti-rheumatic treatment for a study period of 1 year as per Korean AS reimbursement guideline.

In the event of Adalimumab discontinuation, the reason for discontinuation will be collected. If the reason for treatment discontinuation is due to an adverse event, the event will be collected.

The following variables will be collected at baseline, and every follow-up visit thereafter during the study period.

Baseline

- 1) Demographics: Age, Gender, Family History of AS, Co-morbidity
- 2) Previous AS-related medication (medication, dosage)
- 3) Concomitant medication
- 4) BASDAI 50
- 5) Extra-axial symptoms: Enthesitis, Peripheral arthritis and Dactylitis (presence or absence)
- 6) Extra-axial symptoms assessment: MASES, enthesitis of the plantar fascia, TJC^s and SJC^s, Counts of dactylitic digits
- 7) Adalimumab administration

Week 12, 28, 36 and 52 after baseline

**Window period for each follow up visit will be ± 4 weeks.*

- 1) BASDAI 50

- 2) Extra-axial symptom assessment: MASES, enthesitis of the plantar fascia, TJC^s and SJC^s, Counts of dactylitic digits
- 3) The change of AS-related medication (If applicable)
- 4) Extra-axial symptoms excluding Enthesitis, Peripheral arthritis and Dactylitis (If applicable, such as IBD, uveitis, etc.)

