9.7 Data Analysis

The study population will be classified by ITT (Intention-To-Treat) set and PP (Per-Protocol) set.

- ITT set: The ITT set will consist of those patients who have received at least one adalimumab treatment and have assessed EAMs at baseline.

- PP set: The PP set will consist of those patients who meet inclusion/exclusion criteria and complete the study without any major protocol deviation of the patients included in the ITT set.

General Considerations

Continuous variables will be described with the number of patients, arithmetic mean, standard deviation, median, minimum, and maximum. For categorical variables, the frequency and proportion will be presented. The values such as arithmetic mean, standard deviation, and proportion will be rounded to two decimal places. If the observation value is missing value, it will be treated as a missing value in the analysis.

Baseline Characteristics including demographics

Descriptive statistics will be used to present variables regarding demographics and disease/medication related data. Continuous variables will be described with the number of patients, arithmetic mean, standard deviation, median, minimum and maximum. For categorical variables, the frequency and proportion will be presented. The values such as arithmetic mean, standard deviation, and proportion will be rounded to two decimal places.

If the observation value is missing value, it will be treated as a missing value in the analysis. Statistical analyses will be performed using SAS V9.2 or higher.

Primary Endpoint:

The frequency of EAMs of interest at baseline: peripheral arthritis, enthesitis and dactylitis

-The frequency and the proportion of patients who are having peripheral arthritis, enthesitis or dactylitis in Korean AS patients at baseline will be presented, and 95% confidence intervals will be calculated.

Secondary Endpoints:

- The percentage of patients with 50% improvement of baseline BASDAI (BASDAI 50) at week 12, 28, 36, and 52
 - The frequency and the proportion of patients with 50% improvement of baseline BASDAI at week 12, 28, 36, 52 will be presented.
- The change of MASES (Maastricht Ankylosing Spondylitis Enthesitis Score) from baseline to week 12, 28, 36, and 52 in patients who had enthesitis at baseline
 - The descriptive statistics (the number of patients, mean, standard deviation, median, min, max) for MASES according to study visit and the change from baseline at week 12, 28, 36, 52 will be presented.

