- The percentage of patients who have enthesitis of the plantar fascia from baseline to week 12, 28, 36 and 52.
 - The frequency and the proportion of patients who have enthesitis of the plantar fascia at week 12, 28, 36, 52 will be presented.
- The change of dactylitis score from baseline to week 12, 28, 36 and 52 in patients who had dactylitis at baseline.
 - The descriptive statistics (the number of patients, mean, standard deviation, median, min, max) for dactylitis score according to study visit and the change from baseline at week 12, 28, 36, 52 will be presented.
- The change of tender and swollen joint counts (TJC, 0-46; SJC, 0-44) from baseline to week 12, 28, 36 and 52 in patients who had peripheral arthritis (≥ 1 swollen joint) at baseline.
 - The descriptive statistics (the number of patients, mean, standard deviation, median, min, max) for tender and swollen joint counts (TJC, 0-46; SJC, 0-44) according to study visit and the change from baseline at week 12, 28, 36, 52 will be presented.

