Annex 1.

1) Maastricht Ankylosing Spondylitis Enthesitis Score (MASES)

MAASTRICHT ANKYLOSING SPONDYLITIS ENTHESITIS SCORE				JE
The MASES and Additional Enthesitis score should only be completed for patients with Enthesitis at the screening visit. Please grade each enthesis below 0(absent), 1(present)				
		Patient Right		Patient Left
1st Costochondral joint		 0	 1	 0  1
7th Costochondral joint		 0	 1	 0  1
Posterior Superior Iliac Spine		 0	 1	 0  1
Anterior Superior Iliac Spine		 0	 1	 0  1
Iliac Crest		 0	 1	 0  1
Proximal Insertion of Achilles tendon		 0	 1	 0  1
Patient Midline				
5th Lumbar Spinous process		 0		 1
Total				
ADDITIONAL ENTHESITIS SCORE				JE
		Patient Right		Patient Left
Fascia plantaris		 0	 1	 0  1

2) Joint Evaluation

JOINT EVALUATION		JE					
Joint (circle the correct answer)		0=Absent		1=Present			
		Pain/Tenderness		Swollen			
		R	L	R	L	R	L
1. Sternoclavicular		0	1	0	1	0	1
2. Acromio-clavicular		0	1	0	1	0	1
3. Shoulder		0	1	0	1	0	1
4. Elbow		0	1	0	1	0	1
5. Wrist		0	1	0	1	0	1
6. Metacarpophalangeal I		0	1	0	1	0	1
7. Metacarpophalangeal II		0	1	0	1	0	1
8. Metacarpophalangeal III		0	1	0	1	0	1
9. Metacarpophalangeal IV		0	1	0	1	0	1
10. Metacarpophalangeal V		0	1	0	1	0	1
11. Thumb Interphalangeal		0	1	0	1	0	1
12. Proximal Interphalangeal II		0	1	0	1	0	1
13. Proximal Interphalangeal III		0	1	0	1	0	1
14. Proximal Interphalangeal IV		0	1	0	1	0	1
15. Proximal Interphalangeal V		0	1	0	1	0	1
16. Hip		0	1	0	1	N/A	
17. Knee		0	1	0	1	0	1
18. Ankle		0	1	0	1	0	1
19. Metatarsophalangeal I		0	1	0	1	0	1
20. Metatarsophalangeal II		0	1	0	1	0	1
21. Metatarsophalangeal III		0	1	0	1	0	1
22. Metatarsophalangeal IV		0	1	0	1	0	1

[figure not shown]
Adalimumab
P15-238 Protocol
Version 2.0

23. Metatarsophalangeal V	0	1	0	1	0	1	0	1

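### MASES change is summarised in all patients with baseline enthesitis; any plantar-only patients start at MASES 0 and would dilute the mean improvement by at least their share

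*Combined protocol and SAP*

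**What the plan says.** Everything cited here is in the combined protocol and SAP.

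- **Analysis set.** Sections 4.0, 9.1 and 9.7 all define the MASES endpoint as change "from baseline to week 12, 28, 36, and 52 in patients who had enthesitis at baseline". Section 9.7 plans n, mean, SD, median, minimum and maximum for the score at each visit and for its change. No section sets a minimum baseline MASES or plans a breakdown by baseline MASES.
- **Definition of enthesitis.** Section 9.3 asks for at least one inflamed site within the score, continuing "MASES, 0 to 13) or of the plantar fascia of the foot". Either part is sufficient.
- **Scoring.** The MASES form in Annex 1 has a total. The plantar fascia follows under a separate "Additional Enthesitis score". The form "should only be completed for patients with Enthesitis at the screening visit", so a patient who qualifies through the plantar fascia alone is given one and records a MASES of 0.
- **Neighbouring endpoints.** Joint counts are followed "in patients who had peripheral arthritis (≥ 1 swollen joint) at baseline". For dactylitis, section 9.3 states: "Dactylitis will be measured by a simple count of dactylitic digits". Plantar fascia enthesitis has its own endpoint, a proportion at each visit, but this does not take plantar-only patients out of the MASES set.
- **Missing data.** Section 9.2.2: "Once a subject is dropped out from the study, no further information for that subject will be collected". Section 9.7: "If the observation value is missing value, it will be treated as a missing value in the analysis".

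**The concern.** The condition for entering the MASES summary is wider than the score that is then followed. A patient whose only inflamed enthesis is the plantar fascia is in the set but at the floor of the scale, so the change can be zero or positive and never negative. Averaging such patients with those who have room to improve pulls the mean towards zero.

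This endpoint serves the secondary objective on effectiveness for extra-axial manifestations, and the study has no control arm. The mean change is therefore likely to be read as the size of the improvement in enthesitis. The planned minimum of baseline MASES would show that at least one patient started at 0, but not how many did. A reader of the report could not recover the result for patients who had MASES involvement. The plantar-only share may also differ between visits, because drop-outs contribute no further data and missing values stay missing. Part of any difference between visits could then come from a change in the mix of patients.

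**Working it through.** **Check of the score.** Annex 1 lists six bilateral sites and one midline site: 6 × 2 + 1 = 13. This reproduces the 0 to 13 range in section 9.3 and confirms that the plantar fascia is outside MASES. The documents give no expected MASES change, so there is no planned figure to reproduce for this endpoint.

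**Identity.** Let q be the plantar-only share of patients with MASES data at a visit, m the mean change in patients with baseline MASES ≥ 1 (m < 0 is improvement), and w the mean change in plantar-only patients (w ≥ 0, because they start at the floor).

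- Mean in the planned set = (1 − q)·m + q·w
- Absolute shift from m = q·(w − m)
- Relative loss of improvement = q·(1 + w/|m|), which is at least q, and equals q when w = 0

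**Inputs.** The documents give none of q, m or w. All values of them below are assumptions.

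With w = 0, the loss is 5%, 10% or 20% at q = 5%, 10% or 20%, whatever m is. With m = −2.10 and w = 0.15, the shift is 2.25·q:

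| q | Mean change | Shift | Relative loss |
|---|---|---|---|
| 0% | −2.1000 | 0 | 0% |
| 1% | −2.0775 | 0.0225 | 1.1% |
| 2% | −2.0550 | 0.0450 | 2.1% |
| 5% | −1.9875 | 0.1125 | 5.4% |
| 10% | −1.8750 | 0.2250 | 10.7% |
| 20% | −1.6500 | 0.4500 | 21.4% |

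With m = −1.20 and w = 0.15, the relative loss at 5%, 10% and 20% is 5.6%, 11.2% and 22.5%.

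**Median and percentage change.** The assumed model behind m = −2.10 is a baseline of 1 + Poisson(2.5), with each inflamed site persisting with probability 0.4. The improvement is then Bernoulli(0.6) + Poisson(1.5), ignoring the cap at 13. Its mean is 0.6 + 1.5 = 2.10, and its SD is √(0.24 + 1.5) = 1.32.

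- The probability of improving by at most one site is 0.357. At q = 20% it is 0.20 + 0.80 × 0.357 = 0.486 in the planned set. This is below one half, so the median stays at −2.
- Mean change over baseline mean goes from 2.10/3.50 = 60.0% at q = 0 to 1.65/2.80 = 58.9% at q = 20%.

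**Against precision.** Section 9.5 gives 200 patients and 53% enthesitis, so n = 106. In the model the SD of change is 1.32 to 1.49 over q = 0 to 20%, and 1.96·SD/√106 is 0.25 to 0.28. The shift passes that half-width at about q = 12%. With 20% drop-out (n = 106 × 0.80 ≈ 85) it does so at about 14%. These thresholds depend on the assumed SD:

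- SD 2.0: 1.96 × 2.0/√106 = 0.381, and 0.381/2.25 = 17%
- SD 2.5: 1.96 × 2.5/√106 = 0.476, and 0.476/2.25 = 21%

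They also depend on n. The 42.7% enthesitis frequency in sections 4.0 and 7.1 gives 85 patients, or 68 after 20% drop-out, and so higher thresholds still.

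**Share by visit.** With 20% drop-out overall and a proportion d among plantar-only patients, the share at a visit is q·(1 − d)/0.80. A baseline q of 10% becomes 12.5% at d = 0 and 7.5% at d = 40%. The loss is then about 13% and 8% (m = −2.10, w = 0.15).

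**The case against.** The set is the one the protocol defines, and its mean is a valid description of all patients with baseline enthesitis. The word attenuated applies only by comparison with a narrower group. Plantar-only patients may develop MASES sites on treatment, and that is information about enthesitis that should not be discarded. Nothing shows that such patients will be enrolled. No test or confidence interval is planned for this endpoint, the median hardly moves in the assumed model, and response at the plantar fascia is tracked separately. All of this stands. It limits the weight of the point and argues against replacing the planned set, but it does not remove the dilution of the mean whenever q > 0.

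A reader might infer that MASES is the only endpoint with this mismatch. It is not. Swollen joints and dactylitis are selected on the count that is then followed, but the tender joint count is followed in patients selected on at least one swollen joint. Annex 1 scores tenderness and swelling separately, so a patient with a swollen but non-tender joint can enter with a tender joint count of 0.

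Selecting on baseline MASES ≥ 1 also brings regression to the mean. A model with no true change and assumed reliability of 0.95 to 0.80 gives an apparent change of −0.02 to −0.08 in that group. The part added relative to the planned set is 0.004 to 0.015 at q = 2% and 0.011 to 0.037 at q = 5%. At reliability 0.80 that is about a third of the corresponding shifts (0.015/0.045 and 0.037/0.1125). This is a good reason to show both summaries.

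**Conclusion.** The point holds in conditional form. As written, the plan admits plantar-only patients to the MASES-change summary at a score of 0. If any are enrolled, and patients with baseline MASES ≥ 1 improve on average, the mean improvement is smaller than in the latter group by a fraction of at least q. The effect is nil at q = 0 and negligible at 1 to 2%. At shares of 5%, 10% and 20% the loss is 5%, 10% and 20% with w = 0, and slightly more if plantar-only patients worsen. Neither q, m, w nor the SD is in the documents, so the actual size is unknown. The 12 to 14% precision threshold belongs to one assumed SD and sample size.

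Two stronger conclusions are tempting. One is that the planned set is wrong; the documents do not support this, because the set follows the protocol's own definition of enthesitis and is coherent. The other is that the study will understate the improvement in enthesitis; this would require a plantar-only share above zero, which no section establishes. The matter concerns the mean of one descriptive secondary endpoint. The primary frequency of enthesitis and the sample size are unaffected. It is a minor improvement to consider.

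**What to change.** Keep the summary in all patients with baseline enthesitis as the defined endpoint, so that sections 4.0 and 9.1 need no change. Add to section 9.7:

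> MASES change will also be summarised in patients with baseline MASES ≥ 1. The number of patients with baseline enthesitis and baseline MASES 0 will be stated at baseline and, among patients with MASES data, at each visit.

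The added summary should use the same analysis population as the planned one. If the count proves to be zero, the two summaries coincide and the question is closed. Writing this down now also avoids choosing the subset after the data have been seen.

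The cost is one extra table and one count, from data already collected. The added summary has a slightly smaller n and some regression to the mean from selecting on baseline MASES, which stays visible because both summaries are shown.

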9.5 Study Size

The primary endpoint of this study is to investigate the frequency of extra-axial symptoms such as peripheral arthritis, enthesitis and dactylitis in eligible Korean AS patients.

With reference to a study in Korean AS patients^{(1),(3)}, peripheral arthritis, enthesitis and dactylitis were found in 70%, 53% and 1% in AS patients, respectively. We calculated sample size based on the expected frequency of peripheral arthritis and enthesitis.

By assuming 95% confidence interval and 15% confidence interval width, the sample size is estimated at 144 and 171 for peripheral arthritis and enthesitis, respectively. Considering 20% of drop-out rate, about 200 patients will be recruited.

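### The plantar-fascia enthesitis endpoint is worded from baseline but analysed as unpaired visit percentages with no baseline value or stated denominator, so the figure can move either way without any patient changing.

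*Combined protocol and SAP*

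**What the plan says.** Section 9.7 words the endpoint as "The percentage of patients who have enthesitis of the plantar fascia from baseline to week 12, 28, 36 and 52". The analysis line under it reads "The frequency and the proportion of patients who have enthesitis of the plantar fascia at week 12, 28, 36, 52 will be presented". It mentions no baseline figure, change, shift table, subset or denominator.

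The MASES, dactylitis and joint-count endpoints are treated differently. Each is restricted to patients affected at baseline, and each has a change line. For dactylitis, descriptive statistics are promised "for dactylitis score according to study visit and the change from baseline at week 12, 28, 36, 52 will be presented".

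Four other provisions bear on how the plantar-fascia percentages would come out:

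- Missing data (section 9.7): "If the observation value is missing value, it will be treated as a missing value in the analysis".
- Drop-out (section 9.2.2): "Once a subject is dropped out from the study, no further information for that subject will be collected". Only the reason for leaving and serious adverse events are still reported. The listed reasons for drop-out include "In case of Adalimumab discontinuation at any point during study period".
- Expected losses (section 9.5): "Considering 20% of drop-out rate, about 200 patients will be recruited".
- Who is scored (Annex 1): "The MASES and Additional Enthesitis score should only be completed for patients with Enthesitis at the screening visit". The plantar fascia is the additional enthesitis item on that form. Section 9.3 lists the plantar-fascia assessment at baseline and at every follow-up visit with no such limit, and gives its purpose as investigating effectiveness on EAMs.

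Section 9.7 defines an ITT set and a PP set of completers. It does not say which is used for the secondary endpoints.

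**The concern.** A run of visit percentages shows change in patients only if the same patients stand behind each figure, or if those missing resemble those present. Neither is assured here. Patients who stop adalimumab leave the study, and the reason for stopping may be related to how they are doing. A reader who sets the week 52 percentage against a baseline percentage found elsewhere in the report would be comparing all patients with those who remained. The difference would mix real change with a change in who is being counted.

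The Annex 1 limit raises a second, separate problem. Section 9.3 defines enthesitis as at least one inflamed MASES site or plantar-fascia involvement. A patient without enthesitis at the start is therefore negative for the plantar fascia and can change only by becoming a new case. If the form is not completed for such patients, resolutions are recorded and those new cases are not.

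What is at stake is how one secondary effectiveness result is read.

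**Working it through.** **The plan's own figures.** The point rests on no stated result, but the illustration borrows the planned size. Section 9.5 uses a 95% confidence interval of full width 15%, so n = 1.96² × p(1 − p) / 0.075². This gives 144 for p = 0.70 and 171 for p = 0.53, both as stated. With about 200 recruited and 20% drop-out, 200 × 0.20 = 40 leave and 160 remain.

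**Inputs.** N = 200 and drop-out d = 0.20 come from section 9.5. The documents give no plantar-fascia prevalence; p = 20% is assumed, with a range of 10–30%. The ratio r of drop-outs' to completers' baseline prevalence is also an assumption and is varied on both sides of 1. No patient changes status.

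**Formula.** Let q be the prevalence among those who remain. Then p = (1 − d)q + d·r·q, so q = p / [(1 − d) + d·r].

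| r | calculation | observed at week 52 | apparent change |
|---|---|---|---|
| 2 | 0.20 / 1.2 | 16.7% | −3.3 points |
| 1.5 | 0.20 / 1.1 | 18.2% | −1.8 points |
| 1 | 0.20 / 1.0 | 20.0% | 0 |
| 0.5 | 0.20 / 0.9 | 22.2% | +2.2 points |

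Over 10–30% prevalence and 10–30% drop-out, the spurious change runs from −0.9 to −6.9 points at r = 2, and from +0.5 to +5.3 points at r = 0.5.

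**Effect of pairing, in whole patients.** Suppose 40 of 200 are affected at baseline (20%) and 12 of the 40 drop-outs are among them (30%). Those remaining show 28/160 = 17.5%, an apparent fall of 2.5 points. The same 160 patients also had 28/160 = 17.5% at baseline, so the paired change is 0. When nobody changes, this holds for any drop-out pattern.

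**Why the denominator must be stated.** If drop-out is unrelated to plantar-fascia status, 32 affected patients remain. On observed cases this is 32/160 = 20%, with no bias. If 200 were kept as the denominator it would be 32/200 = 16%, a fall of 4 points from the choice of denominator alone.

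**Annex 1.** At the plan's expected 53% with enthesitis, the form would be completed for 200 × 0.53 = 106 patients. The same 40 affected are then 40/106 = 37.7%, not 20%. The drop-out factor is unchanged: at r = 2, 37.7 / 1.2 = 31.4%; at r = 0.5, 37.7 / 0.9 = 41.9%. The other 200 − 106 = 94 patients are never scored. If the percentage is read as applying to all 200, before any drop-out, each new case missed among the 94 lowers it by 1/200 = 0.5 points.

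**The case against.** Several points on the other side stand.

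- **The changing denominator is inferred.** The plan states none. The inference rests on the missing-data and drop-out rules and applies to an observed-case ITT table. The PP set contains completers, so drop-out cannot alter its denominator between visits; that set is fixed but selected.
- **The direction is not given.** A reader might infer that drop-out by itself produces apparent improvement. The documents do not support that. On observed cases it happens only if drop-outs are more often affected than those who stay. Equal prevalence gives no bias, and the reverse pattern looks like worsening. A spurious fall of 7.5 points, from 20% to 12.5%, would need 50% of drop-outs affected, four times the completers' rate, and nothing in the plan suggests such a ratio.
- **A percentage by visit is a possible reading.** This endpoint is called a percentage, while the MASES, dactylitis and joint-count endpoints are called changes. Baseline status is collected, and section 9.7 promises descriptive statistics for disease-related data, so a baseline percentage may well appear. But the plan does not commit to one for this endpoint, and an all-patient baseline would not match the patients left at each visit. BASDAI 50 is also reported as a proportion by visit, but it is a within-patient measure by construction.
- **Pairing is a partial remedy.** It removes the change in composition but still describes only patients who remained on study.
- **Materiality is low.** No test is attached to the endpoint, and the MASES change already gives a within-patient enthesitis measure.

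These points limit the claim. They do not answer the mismatch between endpoint and analysis line, or the conflict between Annex 1 and section 9.3.

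**Conclusion.** The point holds in a limited form. The endpoint is framed from baseline and serves an effectiveness objective, but the planned output has no baseline value, pairing or denominator. In an observed-case ITT table the percentage can shift in either direction with no patient changing: from −3.3 to +2.2 points for ratios from 2 down to 0.5, at an assumed 20% prevalence and the plan's 20% drop-out. These sizes are illustrations, because neither the prevalence nor the drop-out pattern is in the documents.

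The conflict over who is scored needs no assumption about drop-out. If the Annex is followed, new cases in patients without enthesitis at screening go unrecorded, which favours apparent improvement when the endpoint is read as covering all patients.

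Severity is minor and the change is a free improvement. The primary endpoint is measured at baseline and is untouched.

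**What to change.** In section 9.7, replace the plantar-fascia analysis line with the following:

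- The baseline percentage, with its n.
- At each of weeks 12, 28, 36 and 52, a baseline-by-visit table (resolved, persistent, new, never) in patients with both assessments, with n and the paired difference in proportions. A 95% confidence interval is optional, since the plan gives none for the other secondary endpoints.
- The analysis set and denominator, named explicitly.
- A note that the result describes only patients still on study at that visit.

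Then reconcile Annex 1 with section 9.3. Either record the plantar-fascia item for all patients at every visit, or restrict the endpoint explicitly to patients with enthesitis at baseline, as the MASES endpoint already is.

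The cost is a wording change and one table, using baseline data already listed for collection. Scoring all patients also means changing the form's instruction and adds one right/left item per visit for those not now scored. Restricting the endpoint adds no data collection.

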9.0 Research Methods

9.1 Study Design

This is a prospective, mono-country, multi-center study in AS patients treated with adalimumab.

At least 200 subjects will be enrolled at approximately 10 sites.

Physicians will be asked to document on a separate log the number of patients who are possible to participate in this study. Presence or absence of EAMs and decision to participate will be collected.

The baseline assessment should be performed prior to the first dose of adalimumab (Visit1). Study visits will be conducted at 12, 28, 36 and 52 week after baseline. All subjects will have one Follow-up approximately 30days after the last dose of adalimumab.

Primary Endpoint:

- The frequency of EAMs of interest at baseline: peripheral arthritis, enthesitis and dactylitis

Secondary Endpoints:

- The percentage of patients with 50% improvement of baseline BASDAI (BASDAI 50) at week 12, 28, 36, and 52
- The change of MASES (Maastricht Ankylosing Spondylitis Enthesitis Score) from baseline to week 12, 28, 36, and 52 in patients who had enthesitis at baseline
- The percentage of patients who have enthesitis of the plantar fascia from baseline to week 12, 28, 36 and 52.
- The change of dactylitis score from baseline to week 12, 28, 36 and 52 in patients who had dactylitis at baseline.
- The change of tender and swollen joint counts (TJC, 0-46; SJC, 0-44) from baseline to week 12, 28, 36 and 52 in patients who had peripheral arthritis (≥ 1 swollen joint) at baseline.

The prescription of adalimumab is at the discretion of the physician in accordance with clinical practice and label, is made independently from this study and precedes the decision to offer the patient the opportunity to participate in this study.

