9.2 Setting**9.2.1 Selection of Study Population**

Subject will be adults with AS who meet the eligibility criteria.

Inclusion Criteria

- Subject must be an adult ≥ 19 years

- Subject has been diagnosed with ankylosing spondylitis according to the 1984 modified New York criteria for at least 3months
- Subject has active disease defined by a BASDAI score ≥ 4 despite treatment with at least 2 NSAIDs based on Korea AS reimbursement guideline
- Subject is eligible for adalimumab in daily rheumatologic practice
- Subject must provide written authorization form to use personal and/or health data prior to the entry into the study

Exclusion Criteria

- Female subjects who are pregnant or breast feeding
- Subject applies contraindication to any anti-TNF agent
- Subject is participating in other clinical trials

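### The three change-score EAM endpoints cover only baseline-positive patients in an uncontrolled cohort, so regression to the mean mixes with any effect and most new onset goes unanalysed

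*Combined protocol and SAP*

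**What the plan says.** One secondary objective (section 8.0) is to assess how effective adalimumab is on EAMs. Section 9.7 serves it with four analyses:

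- **MASES:** change "from baseline to week 12, 28, 36, and 52 in patients who had enthesitis at baseline".
- **Dactylitis:** "The change of dactylitis score from baseline to week 12, 28, 36 and 52 in patients who had dactylitis at baseline".
- **Tender and swollen joint counts:** change "in patients who had peripheral arthritis (≥ 1 swollen joint) at baseline".
- **Plantar fascia:** "The frequency and the proportion of patients who have enthesitis of the plantar fascia at week 12, 28, 36, 52 will be presented". Neither the endpoint nor its analysis text restricts this by baseline status.

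The first three are descriptive summaries without tests. No analysis of new onset is specified for any EAM.

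On design, section 9.1 states: "This is a prospective, mono-country, multi-center study in AS patients treated with adalimumab". There is no comparator. Entry also selects on activity: "Subject has active disease defined by a BASDAI score ≥ 4 despite treatment with at least 2 NSAIDs" (section 9.2.1). Section 9.9, on limitations, contains only NA.

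On data collection, section 9.3 lists MASES, plantar fascia, both joint counts and dactylitic digits at weeks 12, 28, 36 and 52, whatever the baseline status. It counts a patient as having enthesitis if any MASES site or the plantar fascia is inflamed. The Annex 1 form instead tells sites to fill in MASES and the plantar fascia score only for patients who had enthesitis at screening.

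**The concern.** A group chosen because a fluctuating score was above zero on one day will tend to score lower next time, with or without treatment. The patients left out start at zero and can only stay there or worsen. Reporting only the first group therefore shows one side of the movement between visits, and with no control arm nothing in the study can show how much of that movement is due to selection.

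At stake is the answer to the objective on EAMs. A reader of the final report would see falling scores in affected patients. That reader would have no matching count of patients who developed arthritis, dactylitis or MASES-site enthesitis on treatment, and no stated warning about regression to the mean. The Annex 1 instruction adds a second risk. If sites follow it, enthesitis that starts after screening in a screen-negative patient is not recorded, and no later analysis can recover it.

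**Working it through.** **1. The plan's own figures.** The change endpoints carry no stated figure. The study-size figures (9.5) belong to the baseline-frequency endpoint but confirm the prevalences in use. With n = 1.96² × p(1 − p) / 0.075²:

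- p = 0.70 gives 143.4, so 144.
- p = 0.53 gives 170.1, so 171.

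Both match the plan.

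**2. Patients outside each change analysis, N = 200, as 200 × (1 − p).** Section 9.5 gives 70%, 53% and 1%. Section 7.1 gives 47.1% (a history of peripheral arthritis) and 42.7% (enthesitis). Neither section measures exactly the baseline status used in 9.7, so they serve as a range.

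- Joint counts: 200 × 0.30 = 60, to 200 × 0.529 = 106.
- MASES: 200 × 0.47 = 94, to 200 × 0.573 = 115.
- Dactylitis: 200 × 0.99 = 198, leaving about 2 patients.

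**3. Apparent improvement with no effect.** Assume a score with the same mean m and variance at both visits, linear regression of follow-up on baseline, and between-visit correlation ρ. Patients outside the selected group score zero at baseline, so the baseline mean in the selected group is m/p.

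- Expected change in positives: −(1 − ρ)(m/p − m). As a share of their baseline mean, this is a fall of (1 − ρ)(1 − p).
- Expected change in negatives: +(1 − ρ)m.
- All patients: p × [−(1 − ρ)(m/p)(1 − p)] + (1 − p)(1 − ρ)m = 0. The zero follows from assuming no effect and a stable mean; it is not a finding.

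The documents give no ρ. With assumed values:

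| p | ρ = 0.5 | ρ = 0.7 | ρ = 0.9 |
|---|---|---|---|
| 0.70 (arthritis, 9.5) | 15% | 9% | 3% |
| 0.53 (enthesitis, 9.5) | 24% | 14% | 5% |
| 0.471 (arthritis, 7.1) | 26% | 16% | 5% |
| 0.427 (enthesitis, 7.1) | 29% | 17% | 6% |
| 0.01 (dactylitis, 9.5) | 50% | 30% | 10% |

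A gamma-Poisson simulation of swollen joint counts, with 70% positive and an assumed mean of 2, gave ρ = 0.61. Positives fell by 0.33 from 2.86 (11.5%; the formula gives 0.39 × 0.30 = 11.7%). Negatives rose by 0.78, and the whole cohort changed by about 0.

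**4. Where the formula applies.**

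- **SJC:** directly, because the selection rule is the baseline count itself.
- **MASES:** with dilution. A patient positive only at the plantar fascia enters with MASES 0 and cannot improve. Using enthesitis prevalence as p allows for such patients, provided plantar involvement does not predict later MASES beyond baseline MASES; if it predicts higher scores, the fall is smaller.
- **TJC:** only indirectly. Selection is on swelling, so the size depends on a cross-correlation the documents do not give.

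**5. New onset left unanalysed.** Under the same no-effect model applied to presence or absence, new cases per visit number 200 × (1 − p) × p × (1 − ρ). For p = 0.70 this is 21, 13 and 4 patients at ρ = 0.5, 0.7 and 0.9. For p = 0.53 it is 25, 15 and 5.

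**6. Annex 1 against 9.3 and 9.7.** Section 9.3 schedules enthesitis scoring at every visit, and 9.7 reports plantar fascia involvement with no baseline restriction. If sites follow Annex 1, patients without enthesitis at screening have no form, so that percentage loses its all-patient denominator. Joint counts and dactylitic digits carry no such instruction.

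**The case against.** The strongest reply is that change among affected patients is a legitimate question. Patients without the manifestation cannot improve, so leaving them out loses no information on improvement. The endpoints are secondary and descriptive, and the primary endpoint, baseline frequency, is untouched. That stands, and it is why the baseline-positive summaries should stay. It does not answer the lack of any onset analysis or of any caveat.

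A reader might go further than the documents allow in four ways:

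- **That new-onset EAMs are never counted.** The plantar fascia percentage takes in new cases at that site unless Annex 1 blocks them. New sites, joints or digits in baseline-positive patients enter the change scores. Other EAMs such as uveitis and IBD are collected after baseline, though 9.7 gives no analysis of them.
- **That all the data needed are already in hand.** This is fair for joints and dactylitis under 9.3, but not for enthesitis while Annex 1 stands.
- **That the bias has a known size, or always favours the drug.** The correlations are assumed, and with very stable scores the fall at 70% prevalence is only 3%. Plantar-only patients can move MASES only upwards.
- **That an all-patient mean cures the problem.** It removes only the selection on EAM status. Entry on BASDAI ≥ 4 and the lack of a control remain.

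**Conclusion.** The point holds in limited form. All three change-score EAM endpoints condition on baseline positivity in an uncontrolled cohort, so a fall in scores would combine regression to the mean with any treatment effect. The direction is clear for SJC, diluted for MASES and indirect for TJC. Onset of arthritis, dactylitis or MASES-site enthesitis in baseline-negative patients has no planned analysis.

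The magnitude is illustrative: about 3% to 29% of the baseline mean for arthritis and enthesitis, assuming no effect, a stationary score, correlations of 0.5 to 0.9 and prevalences of 0.427 to 0.70. The dactylitis percentages have little practical meaning, since that endpoint would rest on about 2 patients. The exclusion counts need only the documents' prevalences and N = 200.

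The conflict between Annex 1 and sections 9.3 and 9.7 rests on the text alone. It is the part that could lose data permanently. The sample size is not affected.

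**What to change.** - **9.7, every EAM:** add a baseline-by-visit table (never, resolved, persistent, new onset) in all ITT patients with a baseline value, showing the number not assessed at each visit.
- **9.7, MASES and TJC/SJC:** add the all-patient mean change with a 95% CI. For dactylitis the table is enough; with about 2 expected cases an all-patient mean would say little.
- **Keep** the baseline-positive summaries, labelled as uncontrolled and subject to regression to the mean.
- **9.9:** replace NA with that limitation. State that the all-patient summary neither removes the BASDAI ≥ 4 entry selection nor stands in for a control group.
- **Annex 1:** reconcile it with 9.3 and 9.7 so that enthesitis is scored in all patients at all visits.

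The cost is a few extra tables, one changed form instruction and somewhat more form completion at sites. The reported mean change is likely to look less favourable.
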